Trial Design: This is a single-arm, phase I/II, study of PAC/SIR/TAC for the prevention of acute GVHD after matched related and unrelated alloHCT. First, a standard 3+3 dose escalation method will be performed combining PAC with SIR/TAC. The MTD identified during phase I, as well as serial PK/PD data, will inform the recommended phase II dose. Therefore, the recommended phase II dose will be the lowest dose that decreases the amount of pSTAT3+ CD4+ T-cells <35% at day +21 and does not exceed the MTD (see Table 1). The phase II component is powered to determine if JAK2 inhibition with PAC significantly reduces CD4+ T-cell STAT3 activation early after allogeneic HCT compared to our historical benchmark. Our published study showed the mean CD4+ T-cell STAT3 phosphorylation at day +21 was 50% among all HCT recipients, 70% for those who later developed acute GVHD, versus 32% for those who did not². Therefore, success will be defined as a reduction in CD4+ T-cell STAT3 phosphorylation to 35% or less at day +21. This phosphorylation value not only estimates biologic activity, but also falls within the standard deviation of what was observed among HCT recipients who never acquired acute GVHD². The association of CD4+ T-cell STAT3 phosphorylation and acute GVHD risk is under prospective validation, but currently offers guidance in determining the degree of on-target pathway suppression for HCT recipients on this trial. As pacritinib is a direct inhibitor of JAK2/STAT3 signal transduction, greater reduction in CD4+ T-cell pSTAT3 phosphorylation is possible in this patient population. An initial 24 patients will be treated with PAC/SIR/TAC to investigate whether the biologic activity of STAT3 in CD4+ T-cells is reduced at day +21.

Secondarily, we will monitor enrolled patients for acute GVHD by day +100. To investigate the clinical efficacy of the PAC/SIR/TAC combination in GVHD prevention, the trial will be expanded by an additional 14 subjects if 9 or less of the first 24 patients develop grade II-IV acute GVHD. This expansion threshold is based on our data from the SIR/TAC trial where the cumulative incidence of acute GVHD incidence by day +100 was 43%. PAC/SIR/TAC will be considered favorable if the primary endpoint is met AND ≤12 of the total 38 (31.6%) patients develop acute GVHD by day +100.

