- 9. Grade 3 or higher recent (within the past 6 months) or ongoing bleeding events.

10. Symptomatic or uncontrolled cardiovascular disease, myocardial infarction or severe/unstable angina within the past 6 months, or New York Heart Association Class III or IV congestive heart failure

c. Donor eligibility

Eligible donors will include healthy sibling, relative or unrelated donors that are matched with the patient at HLA-A, B, C, and DRB1 by high resolution typing as defined by the Collaborative Trials Network²⁹.

V. Study Design

1. Sample size

a. A total of up to 12-18 evaluable patients will be enrolled in phase I. The 6 patients treated at the MTD (or lowest biologically active dose) in phase I will be analyzed among those treated in phase II. In phase II, 24 evaluable patients will be enrolled to study CD4+ T-cell STAT3 phosphorylation at the MTD. Additional 14 evaluable patients will be accrued to expansion stage if 9 or less of the initial patients treated at the MTD develop grade II-IV acute GVHD. Thus, a total of up to 50 evaluable patients could be enrolled to the combined phase I and II components of the trial. We anticipate up to 63 total could be enrolled and treated with PAC/SIR/TAC (which would account for a 10% replacement for non-evaluable subjects in phase II, and possible 10 subjects non-evaluable in the phase I component of the trial).

Withdrawal

- a. Subject withdrawal from the study will take place under the following circumstances:
 - i. those patients who sign consent for the study, but fail to initiate treatment on account of:
 - 1. denial of coverage from insurance provider
 - 2. death prior to initiation of treatment
 - 3. withdrawal of patient consent at any time after therapy

Subjects who withdraw consent for pacritinib therapy after day +21 but before day +100 will be asked to continue on study for follow-up of their condition and allow collection of research blood samples. These patients will be considered "off-therapy, on-study" reflecting **partial** withdrawal of consent. These patients will inform the secondary endpoint of GVHD prevention, and only be excluded from the analysis if they are off pacritinib for more than 4 weeks and do not resume the drug thereafter for causes other than acute GVHD (treatment failure). Subjects who withdraw consent for pacritinib therapy before day +21 will be excluded from any study analysis reflecting **full** withdrawal of consent.

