The expanded phase II trial (second stage of phase II) will be considered favorable if 12 or less of the total 38 (31.6%) patients develop acute GVHD by day +100. This sample size was computed using Simon's two-stage design with 10% one-sided significance level and 90% power. If this regimen is actually not effective, there is 9.8% probability of concluding that it is. If the regimen is actually effective, there is 8.6% probability of concluding that it is not. If the second stage is open (n=38), the study will achieve 95% power to detect a decrease of 15% when the SD is 25%. The Blood and Marrow Transplant Program at MCC performs approximately 190 allogeneic procedures annually. A conservative estimated accrual rate of 20% would provide at least 38 patients each year allowing for full accrual by 24 months.

An evaluable patient for primary endpoint is defined as patients who received PAC/SIR/TAC until at least day +21 of their alloHCT and who has neither relapsed nor died of any reasons without experiencing grade II-IV aGVHD until day +100. A non-evaluable PAC/SIR/TAC patient will be replaced and we anticipate 41 patients will be accrued to the interventional study in order to account for 10% of competing risks (relapse or death without GVHD) at day +100.

Additional 15 patients who receive the standard GVHD prevention regimen of SIR/TAC, will be enrolled for blood sample collection only (8 green top tubes of blood) on days +21 and +100 of the alloHCT. The amount of circulating Treg, Th1, and Th17 cells will be analyzed. The exact same eligibility criteria will apply for these subjects.

A total of up to 68 (up to 18 patients in phase I [with the 6 treated at MTD included among those analyzed in phase II] + 32 [PAC/SIR/TAC] + 3 [non-evaluable replacement] +15 [blood sample collection only]) patients will be enrolled.

Statistical analysis methods

Patient baseline characteristics will be summarized using descriptive statistics including mean, median, standard deviation and range for continuous measures and proportions and frequencies for categorical measures. As the primary endpoint of the study, one sample t-test will be employed to examine if pSTAT3 at day +21 is decreased by 15% from historic mean of 50%. A two-sided p-value of <0.05 is considered statistically

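### Evaluability for the day +21 pSTAT3 endpoint depends on events up to day +100, and the GVHD error rates are given without saying whether the 43% and 23% share the counted denominator

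*Combined protocol and SAP*

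**What the plan says.** **Primary endpoint.** Sections III and V.6 set the phase II primary endpoint as STAT3 activity in CD4+ T-cells at day +21. Section V.7 tests it with a one-sample t-test against a historical mean of 50%. The same section defines who is evaluable for that endpoint: treated with PAC/SIR/TAC to at least day +21, and "who has neither relapsed nor died of any reasons without experiencing grade II-IV aGVHD until day +100". Non-evaluable patients are replaced, and 41 are to be accrued to allow for 10% competing risks.

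**Benchmark.** The Trial Design paragraph says mean pSTAT3 "at day +21 was 50% among all HCT recipients", and splits it as "70% for those who later developed acute GVHD, versus 32% for those who did not". No filter on relapse or death is described for these 18 patients.

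**GVHD rule.** The trial expands if at most 9 of 24 develop grade II-IV GVHD and is favorable at 12 or fewer of 38. Section V.1 counts both stages in evaluable patients ("Additional 14 evaluable patients will be accrued to expansion stage"). Trial Design speaks of the first 24 patients, and V.7 of the 24 initially treated. The 43% (Background) and the 23% (V.7) are both worded as cumulative incidences. V.7 states errors of 9.8% and 8.6%.

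**Joint success.** Under Trial Design, the regimen "will be considered favorable if the primary endpoint is met AND" the GVHD count is at most 12 of 38.

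**GVHD estimate.** Statistical analysis methods (V.7) plans a cumulative incidence with relapse and non-relapse mortality as competing risks. It does not name the analysis set.

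**The concern.** A measurement taken at day +21 is kept or discarded according to what happens in the following 79 days. A patient who relapses or dies without grade II-IV GVHD leaves the t-test; one who develops GVHD first stays. The plan itself reports that day +21 pSTAT3 differs by later GVHD, so selecting on later events need not be neutral, and the benchmark is not described as selected in this way.

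For GVHD, removing and replacing GVHD-free patients raises the proportion with GVHD among those counted. If 43% and 23% are rates among all treated patients, the cut-offs are being applied to a population with higher rates than those the design assumed.

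The competing-risk estimate has a related gap. On the V.7 evaluable set no competing event before GVHD remains, because those are the patients removed.

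Both halves of the success rule are exposed, so a reader needs to know how far each could move.

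**Working it through.** **Inputs from the plan.** pSTAT3: null mean 50, target 35, SD 25, n = 24 or 38, two-sided 0.05; subgroup means 32 (no later GVHD) and 70 (later GVHD). GVHD: p0 = 0.43, p1 = 0.23, continue if X1 ≤ 9 of 24, favorable if X1 + X2 ≤ 12 of 38. Competing risk c = 0.10 as stated; the stated 41 accrued for 38 implies 3/41 = 0.073. The values c = 0.05 and 0.15 are my assumptions, to show a range.

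**1. Reproducing the plan's figures.** The probability of a favorable result is P(X1 ≤ 9 and X1 + X2 ≤ 12), with X1 ~ Bin(24, p) and X2 ~ Bin(14, p).
- p = 0.43: 0.0984 (stated 9.8%).
- p = 0.23: 1 − P = 0.0861 (stated 8.6%).
- Noncentral t power for pSTAT3: 80.4% (n = 24, SD 25), 94.0% (n = 24, SD 20) and 95.0% (n = 38, SD 25), matching the stated 80%, 94% and 95%.

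The stated arithmetic is correct. What is open is the population the rates describe.

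**2. pSTAT3 shift.** If a fraction c with mean m is removed from patients with overall mean M, the analysed mean moves by c/(1 − c) × (M − m). Removed patients had no prior grade II-IV GVHD, so the nearest documented value is m = 32.
- M = 50, c = 0.10: 0.1111 × 18 = +2.00 points. SE = 25/√24 = 5.10. The chance of a significant decrease is 1.0% instead of 2.5%.
- M = 50, c = 3/41: 0.0789 × 18 = +1.42 points; 1.3% instead of 2.5%.
- M = 35, c = 0.10: 0.1111 × 3 = +0.33 points; power 78.6% instead of 80.4%.

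Patients lost before day +21 have no sample in either set, so the fraction removed after sampling is below c. For m = 32, these shifts are upper limits at the given c.

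**3. GVHD errors if 43% and 23% are all-treated rates.** With GVHD-free relapses and deaths removed, the rate among those counted is p/(1 − c), taking the same c under both hypotheses.

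| c | 0.43/(1 − c) | False positive | 0.23/(1 − c) | False negative |
|---|---|---|---|---|
| 0.05 (assumed) | 0.453 | 5.8% | 0.242 | 11.8% |
| 3/41 | 0.464 | 4.4% | 0.248 | 13.7% |
| 0.10 (stated) | 0.478 | 3.0% | 0.256 | 16.2% |
| 0.15 (assumed) | 0.506 | 1.3% | 0.271 | 21.9% |

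At c = 0.10 power is 100 − 16.2 = 83.8%, against 90% in the design.

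**4. Offset from early GVHD.** Section V.7 also makes anyone not treated to day +21 non-evaluable, with no exception for GVHD. If such GVHD patients are a fraction e of those treated under the null, the counted null rate is (0.43 − e)/(0.90 − e). For assumed e = 0.03 or 0.05, the false-positive rate is 4.9% or 6.7%. Removing the same share of GVHD cases under the alternative gives false-negative rates of 11.8% or 9.3%. The plan gives no value for e.

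**The case against.** The best defence is that little changes. With the non-GVHD mean of 32%, the pSTAT3 shift is well inside one standard error and makes a false claim less likely. GVHD is a secondary endpoint meant to show whether further study is warranted, and removing only GVHD-free patients lowers its false-positive rate. All of that stands. What it leaves open is a rule that discards valid samples for later events, and a stated GVHD power that may be too high.

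Four stronger readings are tempting, and the documents do not support them.
- A reader might infer that 9.8% and 8.6% hold only if 43% and 23% are evaluable-only rates. They also hold if the rates are all-treated and every treated patient is counted, as the initially-treated wording allows. The early-GVHD offset could bring the false-positive rate back too: at an assumed e = 0.075 it is again 9.8%.
- A reader might infer that false-positive risk is inflated. For GVHD, with all-treated rates at 10% competing risk, this needs early-GVHD removals larger than that 7.5%, and nothing documents such removals. For pSTAT3 it needs removed patients with a mean above the overall mean, such as the 70% of those who later developed GVHD, when these patients left without it.
- A reader might see a contradiction in the Withdrawal subsection, where some patients would "only be excluded from the analysis if they are off pacritinib for more than 4 weeks and do not resume the drug thereafter". That sentence concerns withdrawals after day +21 and the secondary endpoint, while the V.7 rule is labelled for the primary endpoint. The treatment-failure wording has the same scope. What remains is a gap: how a patient with GVHD who stops before day +21 is counted.
- A reader might want every treated patient in the added GVHD estimate. The Withdrawal subsection rules this out: "Subjects who withdraw consent for pacritinib therapy before day +21 will be excluded from any study analysis", as a full withdrawal of consent.

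**Conclusion.** The point holds in limited form. The V.7 rule conditions a day +21 measurement on events to day +100, and nothing elsewhere in the plan repairs it. The effect on pSTAT3 is probably small, and conservative if removed patients resemble the non-GVHD group: at most about +2.0 points at 10% removed and a true mean of 50%, and under 2 percentage points of power at a true mean of 35%. The actual direction is unknown, because the plan gives no pSTAT3 values for such patients.

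For GVHD, 9.8% and 8.6% are right when rates and counts share a denominator. If 43% and 23% are all-treated rates while GVHD-free relapses and deaths are replaced, about 3.0% and 16.2% apply at 10% competing risk. This assumes equal competing risk under both hypotheses and no early-GVHD removals, which would partly offset it by an undocumented amount. The documents do not say how relapse and death were handled in the 43%, so the condition cannot be resolved from them.

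**What to change.** V.6 says accrual is complete, so keep the existing decision set and the 9/24 and 12/38 cut-offs, and add the following.

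1. **pSTAT3.** Define a set by day +21 status only: a valid sample while on PAC/SIR/TAC. The 72-hour criterion used for phase I evaluability in V.7 could serve. Include the pooled phase I patients. Report it beside the current set, labelled as added after accrual.
2. **GVHD error rates.** State which denominator 43% and 23% use and give the matching errors: 9.8%/8.6% if it is the counted set, about 3.0%/16.2% if all-treated with 10% removed.
3. **Competing-risk estimate.** Run it on all treated patients except those the Withdrawal subsection classes as full withdrawal of consent, keeping GVHD-free relapses and deaths as competing events. Label it as added after accrual, and note that it includes patients the 4-week exclusion would leave out.
4. **Wording.** Reconcile the denominators in Trial Design, V.1 and V.7, and state how a patient with grade II-IV GVHD who stops before day +21 is counted.

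The cost is revised text and a few tables, with no new patients or samples. The added results are post hoc and may disagree with the evaluable-only ones, and the stated GVHD power may become less favourable.

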Pacritinib dose at day +69	Day +70 reduction	Day +84 reduction
200mg BID	200mg daily	100mg daily
200mg daily	100mg daily	100mg every other day (QOD)
100mg daily	100mg QOD	100mg on Sunday and

^{*} Patients demonstrating signs/symptoms of heart failure on PAC/SIR/TAC will undergo a 2-D echocardiogram to document the left ventricular ejection fraction. Subsequent echocardiograms will be performed per the discretion of the attending physician based on clinical need.

T ,
Linursday
Tharbady

II. Trial objectives

- a. Primary objectives:
- i. Phase I: Determine the lowest biologically active dose of pacritinib that is safe and well tolerated when combined with SIR/TAC.
- ii. Phase II: Determine if PAC/SIR/TAC suppresses STAT3 activity in circulating CD4+ T-cells at day +21², to at least 35% phosphorylation.

.

- b. Secondary objectives:
 - i. Investigate whether PAC/SIR/TAC reduces the cumulative incidence of acute GVHD by day +100, compared to our published rate of 43% from SIR/TAC alone. This benchmark is bolstered by an ongoing retrospective analysis of 819 patients treated with SIR/TAC, MTX/TAC, or MMF/TAC, where the incidence of acute GVHD with SIR/TAC was similar to rates observed in our trial.
 - ii. Study the effect of PAC/SIR/TAC on Treg, Th1, and Th17 differentiation among circulating T-cells at day +21 and day +100.
 - a) A subset of 15 patients treated with standard SIR/TAC alone who are receiving a matched related or unrelated alloHCT will also be enrolled for blood sample collections only on day +21 and day +100.
 - b) The effects of PAC/SIR/TAC versus SIR/TAC on Treg, Th1, and Th17 development will be investigated.
 - iii. Determine how PAC/SIR/TAC impacts CD28 and IL-2 receptor signal transduction by measuring S6 (mTOR), H3 ser10 (Aurora kinase), and STAT5 phosphorylation in CD4+ T-cells at days +21 and +100. Phosphoprotein values will be compared to SIR/TAC only patients (n=15) enrolled in the sample-only portion of the trial.

III. Trial endpoints

- a. Primary endpoints:
 - i. Phase I: The lowest biologically active dose of PAC that is safe and well tolerated with SIR/TAC
 - ii. Phase II: STAT3 activity in circulating CD4+ T-cells at day +21².
- b. Secondary endpoints (phase II only):
 - i. Cumulative incidence of acute GVHD by day +100
 - ii. Treg, Th1, and Th17 differentiation among circulating T-cells at day +21 and day +100.

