Subjects who do not wish to permit follow-up of their condition and continued collection of their peripheral blood for research studies will also be called **full** withdrawal of consent.

Withdrawal of consent (partial or full) will be documented in OnCore and within the patient's medical record.

3. Intervention: Pacritinib

a. Dose and Schedule: Up to 200mg BID orally (or MTD) from day 0 until day +100. PAC will be tapered to 50% of the total dose at day +70, then 25% of total dose at day +84, then stop at day +100 (+/- 7 day window is provided around timing of tapering events at day +70 and day +84, as well as last dose stop date around day +100).

4. Standard transplant care and practice

a. Donor selection

Donor must be a sibling, relative, or unrelated donor identical for HLA-A, -B, -C, and HLA-DRB1 by high resolution typing methods.

- b. Stem cell mobilization and collection
- 1. Peripheral blood stem cell mobilization: Donors will be mobilized and collected per institutional or National Marrow Donor Program (NMDP) standard operating protocol. The desired target CD34+ cell dose is $5-10 \times 10^6$ cells/kg. Collection of $<5 \times 10^6$ CD34/kg is not a deviation.
- 2. Umbilical cord blood, HLA haploidentical, and bone marrow stem cells grafts are not included in this protocol.

c. Conditioning regimen

The conditioning regimen is per physician discretion but restricted to busulfan and fludarabine or melphalan and fludarabine. The specific details of these two regimens will adhere to BMT Program standards.

Version 8.0 14

d. GVHD prophylaxis

In addition to the study drug, pacritinib, SIR/TAC will be administered and dosed according to Moffitt Cancer Center, Department of Blood and Marrow Transplantation standard practice. Attending physician discretion is permitted with regard to timing, rapidity, and completion of SIR/TAC taper. SIR/TAC levels will be monitored according to program standards. The therapeutic target for SIR is 5-14 ng/ml. The therapeutic target for tacrolimus is 3-7 ng/ml. It is expected that pharmacologic fluctuations of SIR and TAC levels may occur during this treatment, and such fluctuations in dose levels outside the target ranges will not be considered a deviation. Dose modifications of SIR/TAC for concurrent use of CYP3A4 inhibitors or inducers will be based on program standards.

Note: Pacritinib is neither an inhibitor nor an inducer of cytochrome P450 (CTI BioPharma Investigator Brochure).

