significant. If data is not normally distributed, an appropriate transformation (i.e., logtransformation) or nonparametric test will be considered. As the key secondary endpoint, the cumulative incidence of grade II-IV acute GVHD will be estimated using the competing risk approach, where relapse and non-relapse mortality are considered the competing risks. The one-sided 90% confidence interval for grade II-IV acute GVHD will be computed using log-log transformation.

Overall and relapse-free survival (OS and RFS) will be analyzed using the Kaplan-Meier method. The association of time-to-event data with/without competing risks with other potential predictors will be explored by the Cox proportional hazards regression model and the Fine and Gray method³⁹, respectively. Fifteen patients treated with SIR/TAC alone will be enrolled for blood sample collection only on days +21 and +100 of their alloHCT. The effects of PAC/SIR/TAC versus SIR/TAC alone on Tregs, Th1, and Th17 at day +21 and +100 will be compared using the generalized linear model with identity link function, adjusting for the effect of acute GVHD (grade 0-I vs. grade II-IV). In addition, the mixed effect model will be considered to explore the difference in trends between two groups. With a two-sided significance level of 0.05, the sample size of 39 (24 in PAC/SIR/TAC and 15 in SIR/TAC) will have 84% power to detect an effect size (=difference/pooled SD) of 1 between two groups. If the second stage is open, the power will increase to 90% as the sample size of PAC/SIR/TAC increases to 38. No multiplicity adjustment will be considered for secondary and exploratory endpoints.

VI. Data collection and safety monitoring

The Data & Safety Monitoring Plan (DSMP) adopted by the H. Lee Moffitt Cancer Center & Research Institute, Inc. (MCC) will ensure that all clinical research conducted or coordinated by the Cancer Center is scientifically well designed, responsibly managed, appropriately reported and protects the rights and welfare of human participants. The methods and amount of monitoring required are dictated by the degree of risk involved to the individual participants and the complexity of the clinical research. Other entities that will assume responsibility for data and safety monitoring include:

- Principal Investigators (PI)
- The Scientific Review Committee (SRC);
- The Protocol Monitoring Committee (PMC);

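### The PAC/SIR/TAC versus SIR/TAC marker comparison adjusts for no pre-transplant factor, so a systematic difference in donor relation or conditioning would bias it; adding both terms is a cheap improvement

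*Combined protocol and SAP*

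**What the plan says.** The trial is single-arm (Trial Design). The comparator for the immune markers is a separate group giving blood only. Section II.b describes it as "A subset of 15 patients treated with standard SIR/TAC alone who are receiving a matched related or unrelated alloHCT", and Section V.7 says "Additional 15 patients who receive the standard GVHD prevention regimen of SIR/TAC, will be enrolled for blood sample collection only". Section V.7 applies the same eligibility criteria to this group. No section says how the 15 are to be chosen, matched or stratified.

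The analysis is in Statistical analysis methods: "The effects of PAC/SIR/TAC versus SIR/TAC alone on Tregs, Th1, and Th17 at day +21 and +100 will be compared using the generalized linear model". That model has an identity link and one covariate, acute GVHD (grade 0-I against II-IV). A mixed model may also be used for trends, but no covariates are named for it. The sizing takes a two-sided 5% level with 24 pacritinib patients and 15 controls, and claims that this "will have 84% power to detect an effect size (=difference/pooled SD) of 1 between two groups". After expansion, it says, "the power will increase to 90% as the sample size of PAC/SIR/TAC increases to 38".

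Two pre-transplant factors are left open:
- **Donor relation.** Inclusion criterion 2 admits matched related and matched unrelated donors.
- **Conditioning.** Section V.4.c: "The conditioning regimen is per physician discretion but restricted to busulfan and fludarabine or melphalan and fludarabine".

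**The concern.** Secondary objective ii asks what adding pacritinib does to Treg, Th1 and Th17. Without randomisation, the group coefficient answers that only if the groups are alike in whatever else moves the markers, or if the model accounts for the differences. The one covariate in the model cannot do this: acute GVHD occurs after transplant and is an outcome the drug is meant to change. The protocol's other references to covariates lie elsewhere. Further predictors are mentioned for time-to-event outcomes, and stage, timing and pathologic grade for the biopsy analysis. Baseline characteristics are only to be summarised.

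Adjusting for the marker's own baseline value is not available either. Section V.6 plans baseline samples for pacritinib patients, but the SIR/TAC group is sampled only on days +21 and +100.

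If the SIR/TAC group differed systematically in donor relation or conditioning, and these affect the markers, the difference would be reported as a pacritinib effect.

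**Working it through.** **Inputs from the documents.** Two-sided alpha 0.05; 24 v 15, or 38 v 15 after expansion; effect size 1 SD; stated power 84% and 90%.

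**Assumptions, because the documents give no figures.** A binary factor has prevalence 40% in one group and 70% in the other and shifts a marker by 0.5 SD.

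**1. Reproduce the stated power.** Two-sample t-test, noncentrality = d / √(1/n₁ + 1/n₂).
- 24 v 15: √(1/24 + 1/15) = 0.329; 1/0.329 = 3.04; power 84.1% (stated 84%).
- 38 v 15: √(1/38 + 1/15) = 0.305; 1/0.305 = 3.28; power 89.6% (stated 90%).

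The stated figures are those of an unadjusted two-group test.

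**2. Bias without adjustment.** Bias = difference in prevalence × effect on the marker.
- One factor: 0.30 × 0.5 = 0.15 SD.
- Two factors in the same direction: 2 × 0.15 = 0.30 SD.

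**3. False-positive rate with no drug effect.** Same formula, with the bias in place of d.

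| Bias | 24 v 15 | 38 v 15 |
|---|---|---|
| 0.15 SD | 0.15/0.329 = 0.46, 7.3% | 0.15/0.305 = 0.49, 7.7% |
| 0.30 SD | 0.30/0.329 = 0.91, 14.4% | 0.30/0.305 = 0.98, 16.2% |

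A simulation of the one-factor case (5,000 runs) gave 6.8% and 8.3% unadjusted. With the factor in the model it gave 4.5% and 4.9%, and the bias was about zero.

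**4. Chance imbalance only.** Two factors at 50% in both groups, each worth 0.5 SD, unadjusted, no drug effect (40,000 runs): rejection is about 5% for both group sizes. The test keeps its level, because the factors' variation is already in the residual SD.

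**5. Power cost of adjusting.** Variance inflation = 1 + k·w(1−w)·0.3²/v. Here k is the number of unbalanced factors (independent within group), w = n₁/(n₁+15), and v is the pooled within-group variance of a factor. I put 40% in the pacritinib group and 70% in the controls; reversing them changes power by less than half a point. No gain in residual variance is assumed.
- 24 v 15: w(1−w) = 0.237; v = (24×0.24 + 15×0.21)/39 = 0.228. Inflation is 1.09 for one factor and 1.19 for two.
- 38 v 15: w(1−w) = 0.203; v = (38×0.24 + 15×0.21)/53 = 0.232. Inflation is 1.08 and 1.16.

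| Power at effect size 1 | 24 v 15 | 38 v 15 |
|---|---|---|
| Unadjusted | 84.1% | 89.6% |
| Two terms, balanced | 84.0% | 89.5% |
| One factor 40/70 | about 81% | about 87% |
| Both factors 40/70 | 77.4% | 84.8% |

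The case with the largest cost (about 7 and 5 points) is also the one with the 0.30 SD bias.

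**The case against.** Several points on the other side stand.

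- **Chance imbalance is not the problem.** A reader might infer that with only 15 controls any accidental difference in mix invalidates the p-value. Step 4 shows that it does not. The harm needs a systematic difference.
- **Selection is not documented.** A reader might infer that the controls select themselves or are picked in a biased way. The documents do not say how the 15 are chosen, and silence is not evidence of biased selection.
- **The size is assumed.** The section on the centre's sirolimus experience names donor type as one of two likely reasons for different GVHD rates between trials, the other being endoscopy practice. It says nothing about circulating T-cell subsets, and nothing in the documents ties the choice of conditioning regimen to these markers. Against the 1 SD effect for which the comparison is sized, 0.15-0.30 SD is small.
- **The design limits the differences.** Both groups need 8/8 matched peripheral blood grafts, share the same exclusions, and follow the centre's SIR/TAC standard.
- **No decision rests on it.** Expansion and the favourable verdict depend on pSTAT3 and GVHD counts.

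The shared criteria restrict who may enter but do not equalise the mix. The limit to two conditioning regimens stands in the treatment sections, not among the eligibility criteria, so it does not clearly bind the controls. Two covariates are a choice, since age, disease and comorbidity are also free. Donor relation and conditioning are the two that the protocol expressly leaves open, and few terms can be carried with 15 controls.

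**Conclusion.** As written, the model controls for no pre-transplant difference between two non-randomised, unmatched groups, so a systematic difference in donor relation or conditioning would pass into the estimated pacritinib effect. Under the assumed 40%/70% imbalance and 0.5 SD effect per factor, the false-positive rate is about 7-8% for one factor, and 14% (24 v 15) or 16% (38 v 15) for two in the same direction. These figures illustrate what could happen. The documents do not show that the groups differ, and do not allow the bias to be estimated. The stated power is correct for an unadjusted test and is not at issue. This is a cheap improvement to a secondary biological comparison, of modest priority; the primary analysis is unaffected.

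**What to change.** 1. Record donor relation (related or unrelated) and conditioning regimen from the charts of the 15 SIR/TAC patients, with an 'other' category if a control received a regimen outside the two in Section V.4.c.
2. Pre-specify both as terms in the Treg, Th1 and Th17 model. Do the same for the S6, H3 ser10 and STAT5 comparisons, which secondary objective iii calls for but for which Statistical analysis methods names no model.
3. Report the unadjusted result alongside.
4. Describe the comparison as non-randomised, with residual confounding possible from factors not in the model.

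The cost is two chart items for 15 patients and two model terms (a third if 'other' is used), plus the loss of power shown in step 5. No new patients or samples are needed. Section V.6 notes that trial accrual is complete, so matching or randomising the comparison is no longer realistic, and adjustment from the charts is the practical remedy.
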